4. SUBJECT DISPOSITION

4.1. Subject Enrollment and Disposition

A summary of subject enrollment will be provided for each country and investigator within a country by treatment group for each cohort and overall. The summary will present the number and percentage of subjects in the Safety Analysis Set. For each column, the denominator for the percentage calculation will be the total number of subjects analyzed for that column.

A summary of subject disposition will be provided by treatment group for each cohort and overall. This summary will present the number of subjects screened, the number of subjects Randomized/enrolled and the number of subjects in each of the categories listed below.

- Subjects Randomized but Never Treated
- Subjects in Safety Analysis Set
- Subject in Full Analysis Set by Randomized Treatment
- Subject in Full Analysis Set by Actual Treatment
- Subject in Completed study treatment
- Subject in did not complete study treatment with reasons for premature discontinuation of study treatment
- Subject in completed the study
- Subject in did not complete the study with reason for premature discontinuation of study

Among subjects who completed study treatment and who discontinued study treatment, the number and percentage of subjects will be summarized for:

- Who had no HCV posttreatment Week 4 assessment and thereafter (No HCV FU-4 and thereafter)
- Who had HCV posttreatment Week 4 assessment but no HCV posttreatment Week 12 and thereafter (With HCV FU-4 but No FU-12 and thereafter)

If a subject did not have any HCV RNA assessment \geq 21 days after the last dose of any study drug (ie, lower bound of FU-4 visit for HCV RNA data), the subject is categorized as having “No HCV FU-4 and thereafter.” If a subject had the HCV FU-4 assessment but did not have any HCV RNA assessment \geq 70 days after the last dose of any study drug (ie, lower bound of FU-12 visit for HCV RNA data), the subject is categorized as having “With HCV FU-4 but No FU-12 and thereafter.”

In addition, the total number of subjects who were randomized, and the number of subjects in each of the disposition categories listed above will be depicted by a flowchart.

The following by-subject listings will be provided by subject identification (ID) number in ascending order to support the above summary tables:

- Disposition for subjects who complete study treatment and study
- Disposition for subjects who did not complete study treatment and/or study with reasons for premature discontinuation of study treatment and/or study
- Lot number and kit ID (if applicable)

4.2. Extent of Exposure

Extent of exposure to study drug will be examined by assessing the total duration of study drug exposure and the level of adherence to the study drug regimen specified in the protocol.

4.2.1. Duration of Exposure to Study Drug

Total duration of exposure to study drug will be defined as last dose date minus first dose date plus 1, regardless of any temporary interruptions in study drug administration, and will be expressed in weeks using up to 1 decimal place (eg, 4.5 weeks).

The total duration of exposure to study drug will be summarized using descriptive statistics (n, mean, SD, median, Q1, Q3, minimum, and maximum) and using the number of subjects (ie, cumulative counts) and percentage of subjects exposed through the following time periods: baseline (Day 1), Week 1 (Day 7), Week 2 (Day 14), Week 4 (Day 28), Week 10 (Day 70), Week 12 (Day 84), and Week 16 (Day 112), Week 20 (Day 140), and Week 24 (Day 168), with Week 16 to Week 24 for group 4 only. A 3-day window is applied to the last planned on-treatment visit to match with the protocol-specified visit window, ie, Groups 1 -3 subjects will have number of subjects exposed through week 12 calculated as the number of subjects who were exposed study drug for at least 81 days. Similarly, Group 4 subjects will have number of subjects exposed through week 24 calculated as the number of subjects who were exposed study drug for at least 165 days. Summaries will be provided by treatment group for each cohort and overall for the Safety Analysis Set.

4.2.2. Adherence to Study Drug

The presumed total number of tablets administered to a subject will be determined by the data collected on the drug accountability CRF using the following formula:

$$\text{Total Number of Doses Administered} = \\ (\sum \text{No. of Tablets Dispensed}) - (\sum \text{No. of Tablets returned})$$

The level of adherence to the study drug regimen will be assessed based on the total amount of study drug administered relative to the total amount of study drug prescribed at baseline.

The level of adherence will be expressed in percentage using the following formula:

$$\text{Level of Adherence}(\%) = \left(\frac{\text{Total Amount of Study Drug Administered}}{\text{Total Amount of Study Drug Prescribed at baseline}} \right) \times 100$$

Note: If calculated adherence is greater than 100%, the result will be set to 100%.

In this study, the total amount of LDV/SOF/±RBV (90/400 mg, ±RBV total 1000-1200mg divided BID if prescribed) prescribed for 12 weeks or 24 weeks (for group 4), total number of tablets needed for LDV/SOF and RBV is as specified in [Table 4-1](#).

Table 4-1. LDV/SOF and RBV tablets needed for each group

	Cohort 1		Cohort 2	
	Group 1 LDV/SOF 12 Weeks	Group 2 LDV/SOF+RBV 12 Weeks	Group 3 LDV/SOF+RBV 12 Weeks	Group 1 LDV/SOF 24 Weeks
LDV/SOF Tablets	84	84	84	168
RBV Tablets	NA	5x84 (420) for baseline weight < 75 kg 6x84 (504) for baseline weight >=75 kg	5x84 (420) for baseline weight < 75 kg 6x84 (504) for baseline weight >=75 kg	NA

Subjects who prematurely discontinue study drug for lack of efficacy (ie, virologic failure) will have the total amount of study drug prescribed calculated up to the first date when virologic failure criteria were met. For virologic failure confirmed by 2 consecutive measurements the date of the first measurement will be used. If there are study drug bottles dispensed on or after the subject first met virologic failure criteria, these bottles will not be included in the calculation of adherence. If a bottle is dispensed and the bottle is returned empty, then the number of tablets returned will be entered as zero. If a bottle is dispensed but not returned (missing), the number of tablets taken from that bottle will be counted as zero.

Descriptive statistics for the level of adherence (n, mean, SD, median, Q1, Q3, minimum, and maximum) with the number and percentage of subjects belonging to adherence categories (eg, {< 80%, \geq 80 to < 90%, \geq 90%}) will be provided for the regimen and for each individual study drug by treatment group for each cohort and overall for the Safety Analysis Set. Categorical displays will be provided for the number of subjects who are at least 80% adherent to their drug regimen (ie, adherence is \geq 80% for each of the study drugs). No inferential statistics will be provided for duration of exposure and adherence to study drug.

A separate by-subject listing of study drug administration and drug accountability will be provided by subject ID number (in ascending order) and visit (in chronological order).

4.3. Protocol Deviations

A summary of important protocol deviations will be provided by the Clinical Operations group for subjects in the Safety Analysis Set.

Subjects who received study drug other than their treatment assignment at randomization or enrollment will be listed with the start and stop dates that they received incorrect study treatment.

5. BASELINE CHARACTERISTICS

5.1. Demographics

Subject demographic variables (ie, age, sex, race, ethnicity, and region) will be summarized. Age will be summarized by descriptive statistics (n, mean, SD, median, Q1, Q3, minimum, and maximum). Age categories (< 65 years, \geq 65 years), sex, race, ethnicity and region will be summarized by the numbers and percentages of subjects. Age is calculated in years at the date of initial study drug administration. If a subject did not receive study drug after enrollment or randomization, the subject's age will be calculated from the date that the subject signed the informed consent form. The summary of demographic data will be provided for the Safety Analysis Set and for the FAS by randomized treatment.

A by-subject demographic listing, which includes the date the informed consent was signed, will be provided by subject ID number in ascending order.

5.2. Baseline Characteristics

Baseline data is defined as data collected on Day 1 predose or last available data collection in the screening period, if not collected on Day 1. Summarization on baseline characteristics will be also performed on the Safety Analysis Set and on FAS by randomized treatment. Baseline characteristics include:

- Body mass index (BMI; in kg/m^2) as a continuous variable and as categories (< 30 kg/m^2 , \geq 30 kg/m^2)
- HCV subgenotype (1 and further specified if coded as 1a, 1b or No confirmed subtype; 4, others if collected)
- IL28B (CC, Non-CC, further specify Non-CC with CT, TT)
- baseline HCV RNA (\log_{10} IU/mL) as a continuous variable and as categories (< 800,000 IU/mL, \geq 800,000 IU/mL)
- Baseline RAVs (yes, no, not-determined)
- Baseline albumin (\leq 3.5 g/dL, $>$ 3.5 g/dL)
- baseline platelets (\leq 75,000/ μ L, 75,000 - \leq 100,000/ μ L, $>$ 100,000/ μ L)
- Prior HCV treatment experience (treatment naïve, treatment experienced) as categorical variable. For treatment experienced subjects, summarizations on the most recent HCV treatment combinations (SOF + SMV, SOF + SMV + RBV, SOF + RBV, SOF + PEG + RBV), and on prior HCV treatment response (Non-Responder, Relapse/Breakthrough, Other with specific reasons) will be provided.

- Estimated glomerular filtration rate (eGFR) using the Cockcroft-Gault equation. eGFR will be calculated by the Cockcroft-Gault method: $eGFR_{CG} \text{ (mL/min)} = [(140 - \text{age (yrs)}) \times \text{weight (kg)} \times (0.85 \text{ if female})] / (\text{serum creatinine (mg/dL)} \times 72)$, where weight is total body mass in kilograms.

These baseline characteristics will be summarized using descriptive statistics (n, mean, SD, median, Q1, Q3, minimum, and maximum) for continuous variables and using the numbers and percentages of subjects for categorical variables.

A by-subject listing of other baseline characteristics will be provided by subject ID number in ascending order.

A separate by-subject data listing for cirrhosis determination and prior HCV treatment and response will be provided for all subjects at screening.

5.3. Baseline Fibrosis Stage

The baseline fibrosis stage is determined using liver biopsy results. Once the liver biopsy results are not available, the Fibrotest results are used instead, with the cut off values of 0.21, 0.31, 0.58, and 0.72 for F0, F1, F2, F3, and F4 respectively.

The baseline fibrosis stage will be summarized as categorical variable. Summarization will be performed on the Safety Analysis Set and on FAS by randomized treatment. The 2-sided 95% exact CI of the proportion based on Clopper-Pearson method will be provided {[Clopper 1934](#)}.

A by-subject listing of the baseline fibrosis stage will be provided by subject ID number in ascending order.

5.4. Medical History

Medical history collected at screening will be coded using the most recent available Medical Dictionary for Regulatory Activities (MedDRA). Medical history will be summarized by system organ class (SOC), preferred term (PT), treatment group for each cohort, and overall. Subjects who report 2 or more medical history items that are coded to the same SOC and/or PT will be counted only once by the unique coded term in the summary. The summary will be provided for the Safety Analysis Set. No inferential statistics will be generated.

A by-subject listing of disease-specific medical history will be provided by subject ID number (in ascending order) and medical history of abnormalities (in chronological order).

6. EFFICACY ANALYSES

All the efficacy analyses are conducted on FAS by randomized treatment and on FAS by actual treatment, unless specified otherwise.

6.1. Primary Efficacy Endpoint

6.1.1. Definition of the Primary Efficacy Endpoint

The primary efficacy endpoint is SVR12 defined as HCV RNA < LLOQ (ie, < 15 IU/mL) 12 weeks after discontinuation of the study drug in the FAS. The COBAS® AmpliPrep/COBAS® TaqMan® HCV Quantitative Test, version 2.0 will be used to measure HCV RNA. HCV genotype and subtype will be determined using the Siemens VERSANT® HCV Genotype INNO-LiPA 2.0 Assay, or other alternative assay decided by Gilead.

6.1.2. Summary for the Primary Efficacy Endpoint

The primary efficacy endpoint is SVR12 (HCV RNA < LLOQ 12 weeks after discontinuation of therapy). The primary analysis will be performed after all enrolled subjects have been followed through 12 weeks posttreatment or discontinued from study.

In the primary efficacy analysis, the SVR12 rate will be summarized by FAS by randomized treatment and by FAS by actual treatment, the 2-sided 95% exact CI of SVR12 based on Clopper-Pearson method will be provided {[Clopper 1934](#)}.

In Cohort 1, a non-inferiority test of SVR12 rates will be performed comparing Group 1 and 2. A non-inferiority margin of 10% will be applied. Non-inferiority will be established if the lower bound of the 2-sided 95% confidence interval (CI) of the difference in SVR12 (Group 1 - Group 2) is greater than -10%. The CI will be constructed using stratum-adjusted Mantel-Haenszel (MH) proportions, stratified by the randomization stratification factors (i.e., genotype 1 or 4; prior SOF therapy in combination with SMV or without SMV).

A similar non-inferiority tests of SVR12 rates will be performed comparing Group 3 and 4 in Cohort 2. The NI margin of 10% is chosen primarily based on clinical judgment. The statistical justification of a NI margin is based on a two-step process in which: 1) we estimate the treatment benefit of the control regimens (LDV/SOF + RBV for 12 weeks for cohort 1; LDV/SOF for 24 weeks for cohort 2) and the historical control (M1), and 2) we define a margin which preserve some fraction of the treatment benefit characterized in Step 1 above (M2).

The M1 and M2 in the current study design as follows:

- M1 = the smallest treatment benefit of the control regimens over the historical control
- M2 = 50% of M1

Based on the Phase 2 ELECTRON-2, GS-US-337-1118, and SYNERGY data, the SVR12 rates for LDV/SOF + RBV for 12 weeks are summarized below:

Table 6-1. Summary of SVR12 Rates in Phase 2 Studies

Study	SVR12 Rates			
	LDV/SOF 12 Weeks		LDV/SOF + RBV 12 Weeks	
Electron-2			n/a	Without cirrhosis: 100% (19/19)
GS-US-337-1118			With cirrhosis: 100% (14/14)	Without cirrhosis: 100% (36/36)
SYNERGY	Advanced liver disease (Knodell score 3, 4) 100% (7/7)	Other (Knodell score 0, 1) 100% (7/7)		
Overall	100% (7/7) 95% CI: (59%, 100%)	100% (7/7) 95% CI: (59%, 100%)	100% (14/14) 95% CI: (77%, 100%)	100% (55/55) 95% CI: (94%, 100%)

The smallest treatment benefit of LDV/SOF 12 weeks and LDV/SOF + RBV 12 weeks are 59% and 77%, respectively (the smaller lower bound of the two 95% CIs).

Note: SVR12 rate of LDV/SOF for 24 weeks is assumed to be at least as high as that of LDV/SOF for 12 weeks.

Since there is no approved standard of care in this patient population, a spontaneous SVR12 rate of at most 5% is assumed as the historical control rate. Using the smallest treatment benefit for the control regimens (ie, the smaller of 59% and 77%) and the highest spontaneous SVR12 rate of the historical control, $M1=59\%-5\%=54\%$. Based on these conservative estimates, a 10% NI margin would retain at least ensure at least 81.5% of the treatment benefit of LDV/SOF + RBV for 12 weeks or LDV/SOF for 24 weeks over the historical control.

However, due to the actual sample size for this study is much smaller than the originally planned sample size, the tests are for exploratory purpose only and the interpretation needs to be cautious since the actual sample size does not have enough power for the test.

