1.3. Sample Size and Power

Cohort 1: For the non-inferiority comparison of SVR12 in the noncirrhotic cohort (group 1 vs. 2) with a 10% non-inferiority margin, a sample size of 90 subjects per treatment group will provide at least 90% power to establish non-inferiority at 1-sided 0.025 level, assuming the SVR12 rates are 98% for both groups.

Cohort 2: For the non-inferiority comparison of SVR12 in the compensated cirrhotic cohort (group 3 vs. 4) with a 10% non-inferiority margin, a sample size of 125 subjects per treatment group will provide at least 90% power to establish non-inferiority at 1-sided 0.025 level, assuming the SVR12 rates are 95% for both groups.

However, the study was early terminated after 87 subjects were enrolled due to lack of feasibility of enrolling originally planned 430 subjects.

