6.4.2. Change on Sample Size

The initial sample size planned was 430, with 90 each in groups 1 and 2, and 125 each in group 3 and 4 to obtain a 10% non-inferiority margin at 1-sided 0.025 level and 90% power, for the comparisons between group 1 and 2, and between group 3 and 4.

Due to lack of feasibility of enrolling subjects, the study was early terminated after 87 subjects enrolled, with 17, 17, 26, 27 randomized in groups 1-4 respectively. Five subjects randomized were never dosed so final analyses set has only 82 subjects (15, 17, 26, 24 for randomization groups 1-4 respectively, while 16, 17, 25, 24 for actual treatment groups 1-4 respectively). Details for subjects with different treatment groups in the two FAS populations are specified in Section 6.4.1.

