6.4.3. Non-inferiority Comparisons

Although the non-inferiority comparisons of SVR12 in the non-cirrhotic cohort (group 1 vs. 2) and in the compensated cirrhotic cohort (group 3 vs. 4) were performed, the results are for exploratory purpose only and the interpretation needs to be cautious since the actual sample size does not have enough power for the test.

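### SAP 6.1.2 decides non-inferiority from a Mantel-Haenszel interval with no stated variance and no rule for 100% response; at the final sample sizes the verdict can turn on that unstated choice

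*SAP*

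**What the plan says.** Section 6.1.2 keeps a formal decision rule: "Non-inferiority will be established if the lower bound of the 2-sided 95% confidence interval (CI) of the difference in SVR12" lies above -10%. For the interval it says: "The CI will be constructed using stratum-adjusted Mantel-Haenszel (MH) proportions, stratified by the randomization stratification factors". The factors are genotype (1 or 4) and prior SOF with or without SMV. Cohort 2 is to be tested in a similar way.

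Section 6.4.2 gives the analysed group sizes: "15, 17, 26, 24 for randomization groups 1-4 respectively, while 16, 17, 25, 24 for actual treatment groups 1-4 respectively". Section 6 applies the analysis to both versions of the FAS: "All the efficacy analyses are conducted on FAS by randomized treatment and on FAS by actual treatment". The planning rates in section 1.3 are high: "assuming the SVR12 rates are 98% for both groups" in Cohort 1 and "assuming the SVR12 rates are 95% for both groups" in Cohort 2.

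Sections 3.5, 6.1.2 and 6.4.3 call the comparisons exploratory. The stated reason for caution in 6.1.2 is that "the interpretation needs to be cautious since the actual sample size does not have enough power for the test", and 6.4.3 says much the same: "the results are for exploratory purpose only and the interpretation needs to be cautious since the actual sample size does not have enough power".

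The text shown contains no variance estimator, continuity correction, all-responder rule or empty-stratum rule for the difference. The only method reference, in section 8, is Clopper-Pearson, which serves the single-group rates.

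**The concern.** Mantel-Haenszel (MH) weighting fixes the point estimate, not the interval. The usual variance is built from p(1-p) in each arm, which is zero when everyone responds. That outcome is foreseeable here: the planning rates are 95-98%, and every Phase 2 cell in Table 6-1 is 100%. The interval then has zero width and NI is declared whatever the sample size. A programmer who adds a correction, or uses score limits, can get the opposite verdict from the same data.

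The caveat also points only one way. A reader told that power is low expects NI to be missed. With an uncorrected interval at these sizes, NI can also be declared too easily.

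**Working it through.** **Inputs.** Margin 10% and two-sided 95% interval (6.1.2). Arms, test vs control, randomized FAS: 15 vs 17 and 26 vs 24; by actual treatment: 16 vs 17 and 25 vs 24 (6.4.2). Planning rates 98% and 95%; planned sizes 90 and 125 per group (1.3). About 5% genotype 4 and 50% prior SMV (1.2). Stratum counts are not given, so every stratified figure below rests on assumed strata.

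**1. The plan's own power figure.** Using power = Φ(0.10/SE - 1.96):
- 90 per group at 98%: SE = √(2×0.98×0.02/90) = 0.0209, power 99.8%.
- 125 per group at 95%: SE = √(2×0.95×0.05/125) = 0.0276, power 95.2%.

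The score (Farrington-Manning) formula gives 93.7% and 89.1%. The claim of at least 90% is reproduced, apart from about one point in Cohort 2 under the score formula. The planned size is not the issue.

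**2. Chance that everyone responds.** Cohort 1: 0.98^32 = 52%. Cohort 2: 0.95^50 = 7.7%.

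**3. Lower limit when everyone responds (difference = 0).**
- *Uncorrected MH or Wald:* variance 0, limit 0% in both cohorts, NI declared.
- *Half-success variance*, p\*(1-p\*)/(n-1) with p\* = (x+0.5)/(n+1). Cohort 1: 1.96×√(0.03027/14 + 0.02701/16) = 12.2%. Cohort 2: 1.96×√(0.01818/25 + 0.0196/23) = 7.8%.
- *The same within two assumed SMV strata* (8+7 vs 9+8; 13+13 vs 12+12): -17.1% and -10.9%. For Cohort 2: 1.96×√[(0.03444/12 + 0.03698/11)/2] = 10.9%.
- *Miettinen-Nurminen:* at full response the limit is -k/(1+k), with k = 1.96²×N/[(N-1)n] and n the test-arm size. Cohort 1: k = 0.264, limit -20.9%. Cohort 2: k = 0.151, limit -13.1%. With the same two strata: -21.5% and -13.3%.

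| Method | Cohort 1 | Cohort 2 |
|---|---|---|
| Uncorrected | 0%, NI | 0%, NI |
| Half-success, pooled | -12.2%, not NI | -7.8%, NI |
| Half-success, within assumed strata | -17.1%, not NI | -10.9%, not NI |
| Miettinen-Nurminen, unstratified | -20.9%, not NI | -13.1%, not NI |

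**4. Not only at 100%.** At 15/15 vs 16/17 the uncorrected limit is 5.9% - 1.96×√(0.0554/17) = -5.3%; the score limit is -15.7%. At 25/26 vs 22/24 they are -8.8% and -12.0%.

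**5. False NI under the uncorrected rule at a true 10-point deficit (nominal 2.5%).** With control at 100%, one test-arm failure already misses the margin (-19.3% in Cohort 1, -11.2% in Cohort 2). The rate is therefore the chance of no failures: 0.9^15 = 20.6% and 0.9^26 = 6.5%. Exact enumeration gives the other unstratified values. The stratified ones are simulated with 5% genotype 4 and 50% SMV.

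| Control rate | 100% | 98% | 95% |
|---|---|---|---|
| Cohort 1, unstratified | 20.6% | 14.7% | 8.9% |
| Cohort 1, assumed strata | 22% | 16% | 10% |
| Cohort 2, unstratified | 6.5% | 4.7% | 4.2% |
| Cohort 2, assumed strata | 8-12% | 6-8% | 5-6% |
| Cohort 1, actual treatment, unstratified | 18.5% | 12.9% | 7.6% |
| Cohort 2, actual treatment, unstratified | 7.2% | 5.3% | 4.8% |

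The stratified ranges in Cohort 2 cover the plug-in and Sato variances. Unstratified Miettinen-Nurminen stays at or below about 2.5% in all four comparisons for control rates of 90-100%. At the planned sizes the uncorrected rule gives 4.4% (control 98%, 90 per group) and 3.2% (control 95%, 125 per group).

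**6. Chance of declaring NI at the planning rates.** Cohort 1: 74-75% uncorrected, 0.5-3% half-success, 0.3% Miettinen-Nurminen. Cohort 2: 39-46%, 18-31% and 23%. Uncorrected and score verdicts disagree (unstratified) in 73.5% of Cohort 1 trials and 16% of Cohort 2 trials.

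**The case against.** The strongest reply is that no decision rests on these tests. The SAP calls them exploratory in three places, and the per-arm Clopper-Pearson limits show the imprecision. If all respond, the lower limits are 78% and 80% in Cohort 1 and 87% and 86% in Cohort 2. That lowers the severity. It does not tell the reader that a (0, 0) difference is an artefact, and the rule for establishing NI is still in force.

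Second, the choice between the two common MH variances (Greenland-Robins and Sato) changed no verdict in the outcome patterns tried. This is right: the missing zero-variance rule and the choice of Wald or score limits do the work. Miettinen-Nurminen is also a different interval from a plain MH one, so 74% against 0.3% measures method choice rather than ambiguity within MH. Among corrections alone the verdict still splits. At full response in Cohort 1, a continuity-corrected Wald limit is -½(1/15 + 1/17) = -6.3% and meets the margin, while the half-success limit does not.

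Third, the effect is conditional. With one test-arm failure and none or one in control, every method tried misses the margin.

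Fourth, Cohort 2 is affected less, and its stratified half-success result depends on assumed strata. With control at 100%, the uncorrected rule gives 6.0% false NI even at 125 per group, against 6.5% at 26 vs 24. Small size is therefore not the main cause there. These limits stand and are reflected in the conclusion.

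**Conclusion.** The concern holds. The SAP does not fix the interval that decides its NI verdict, and the usual uncorrected reading declares NI automatically when everyone responds. At the SAP's own rate, that outcome has probability 52% in Cohort 1.

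The problem is material in Cohort 1, with false NI of about 9-21% unstratified for control rates of 95-100%. It is moderate in Cohort 2, at 4-6.5% unstratified and 5-12% under assumed strata.

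Even 100% response in both arms cannot exclude a 10-point deficit at the 2.5% level. A test arm with a true rate of 90% would show no failures with probability 20.6% (n = 15) or 6.5% (n = 26). A caveat about power alone does not convey this.

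The all-responder and unstratified results need no assumption about strata; the stratified figures do. Given the exploratory status, this should be corrected but does not undermine the descriptive results.

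**What to change.** In 6.1.2, for both cohorts, name the stratified Miettinen-Nurminen score interval for the SVR12 difference, with the existing factors. State what happens to a stratum with no subjects in one arm, for example pooling it with genotype 1 of the same SMV status. This will probably be needed: 5% genotype 4 means about 1.6 of 32 and 2.5 of 50 subjects. The margin and decision rule can stay.

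In 6.1.2 and 6.4.3, add to the caveat that a Wald-type interval risks false NI here, most of all in Cohort 1. Add that with a score interval even 100% SVR12 in both arms gives lower limits of about -21% and -13%, so NI cannot be shown at full response.

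The cost is one sentence on the interval, one on empty strata and two caveat edits. The bound becomes less favourable: the chance of declaring NI in Cohort 1 at 98% in each arm falls from about 74% to 0.3%. Section 6.4.3 speaks of the comparisons as already performed. If results have been seen, the CSR should record the change as made afterwards and show both intervals.

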1.2. Study Design

This is a Phase 3b, multicenter, open label study in adult male and female subjects with chronic genotype (GT) 1 or 4 hepatitis C virus (HCV) infection and who have failed prior SOF-based HCV therapy, including in combination with simeprevir (SMV) \pm RBV or with RBV \pm pegylated interferon (PEG).

Approximately 50% of subjects enrolled may have had prior treatment with SOF + SMV \pm RBV. Approximately 5% of subjects may be infected with GT 4 HCV.

Approximately 430 subjects are planned to enroll into 2 cohorts:

- **Cohort 1:** subjects without cirrhosis (n=180) will be randomized in a 1:1 ratio into Group 1 and 2:

Group 1: LDV/SOF FDC tablet (LDV 90 mg/SOF 400 mg) once daily for 12 weeks

Group 2: LDV/SOF FDC tablet (LDV 90 mg/SOF 400 mg) once daily and RBV at a total daily oral dose of 1000-1200 mg divided twice a day (BID) for 12 weeks

- **Cohort 2:** subjects with compensated cirrhosis (n=250) will be randomized in a 1:1 ratio into Groups 3 and 4:

Group 3: LDV/SOF FDC tablet (LDV 90 mg/SOF 400 mg) once daily and RBV at a total daily oral dose of 1000-1200 mg divided BID for 12 weeks.

Group 4: LDV/SOF FDC tablet (LDV 90 mg/SOF 400 mg) once daily for 24 weeks

Randomization will be stratified by genotype 1 or 4, and by prior SOF therapy in combination with SMV or without SMV

The schedule of assessments is provided as an appendix to the SAP ([Appendix 2](#)).

The total time to complete all study visits is up to approximately 42 or 54 weeks (group 4 only) including the following periods:

- Up to 42-day (6-week) screening period
- A 12-week treatment period for Groups 1 - 3, and 24-week treatment period for Group 4
- Up to 24-week posttreatment period

The study was early terminated after 87 subjects were enrolled due to lack of feasibility of enrolling originally planned 430 subjects.

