3.2. Subject Grouping

For analyses based on the All Randomized/Enrolled Analysis Set or FAS by Randomized Treatment, subjects will be grouped according to the treatment to which they were randomized. For analyses based on other analysis sets, such as the Safety Analysis Set and FAS by actual treatment, subjects will be grouped according to the actual treatment received. The actual treatment received is defined as the randomized treatment except for subjects who received treatment that differs from the randomized treatment for the entire treatment duration. In this case, the actual treatment received is defined as the treatment received for the entire treatment duration.

Randomized Treatment groups will be:

1. Cohort 1 subjects received LDV/SOF 12 week
2. Cohort 1 subjects received LDV/SOF + RBV 12 weeks
3. Cohort 2 subjects received LDV/SOF + RBV 12 week
4. Cohort 2 subjects received LDV/SOF 24 weeks

Due to randomization errors, cirrhotic subjects might be included in cohort 1 and non-cirrhotic subjects might be included in cohort 2 for some efficacy analyses by randomized treatment group.

Actual Treatment groups will be:

1. Cohort 1 Non-cirrhotic subjects received LDV/SOF 12 week
2. Cohort 1 Non-cirrhotic subjects received LDV/SOF + RBV 12 weeks
3. Cohort 2 Cirrhotic subjects received LDV/SOF + RBV 12 week
4. Cohort 2 Cirrhotic subjects received LDV/SOF 24 weeks

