3.3. Strata and Covariates

Approximately 430 subjects will be enrolled into 2 cohorts. In each cohort, subjects will be randomized at a 1:1 ratio into two treatment groups (Non-cirrhotic subjects for cohort 1 and Cirrhotic subjects for cohort 2) via the interactive web response system (IWRS) using a stratified randomization schedule.

Stratification will be based on the following variables:

- HCV genotype 1 or 4
- Prior SOF therapy in combination with SMV or without SMV

If there are discrepancies in stratification factor values between the IWRS and the clinical database, the values recorded in the clinical database will be used for analyses and a listing is provided to document those discrepancies.

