3.5. Multiple Comparisons

No multiplicity adjustment will be made for testing since the statistical comparisons performed are for exploratory purpose only between group 1 vs group 2, and between group 3 vs group 4 due to small sample size actually enrolled.

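### Does the stratified Mantel-Haenszel comparison need a rule for genotype strata that have subjects in only one arm?

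*SAP*

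**What the plan says.** Section 6.1.2 specifies a non-inferiority comparison of Group 1 with Group 2, and a similar one of Group 3 with Group 4. Each uses a 10% margin and a 95% interval from stratum-adjusted MH proportions, "stratified by the randomization stratification factors (i.e., genotype 1 or 4; prior SOF therapy in combination with SMV or without SMV". Two binary factors crossed give four strata in each cohort.

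Four other places bear on how full those strata are:
- Section 1.2: "Approximately 5% of subjects may be infected with GT 4 HCV". It also says that about half of the subjects may have had prior SOF + SMV.
- Section 3.3: subjects are randomized "via the interactive web response system (IWRS) using a stratified randomization schedule". Where IWRS and database stratum values differ, "the values recorded in the clinical database will be used for analyses and a listing is provided to document those discrepancies".
- Section 3.2: "Due to randomization errors, cirrhotic subjects might be included in cohort 1 and non-cirrhotic subjects might be included in cohort 2".
- Section 6.4.2: enrolment stopped at 87, "with 17, 17, 26, 27 randomized in groups 1-4 respectively". After five undosed subjects are removed, the Full Analysis Set (FAS) by randomized treatment has 15, 17, 26 and 24.

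On the standing of the tests, Section 3.5 says that "the statistical comparisons performed are for exploratory purpose only". Section 6.1.2 adds that "the tests are for exploratory purpose only and the interpretation needs to be cautious", and Section 6.4.3 repeats the point. None of these sections mentions a stratum that is empty in one arm.

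**The concern.** Four strata suited cohorts of 180 and 250. With 32 and 50 analysed subjects and genotype 4 at about 5%, the two genotype 4 strata in a cohort would hold roughly one subject each. A stratum with one subject has no comparator, whatever the block size. Stratified randomization therefore reduces the problem but cannot remove it. Reassigning strata from the clinical database, and the cohort errors acknowledged in Section 3.2, can upset block balance further.

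The MH difference gives such a stratum no weight, so the comparison could rest on fewer subjects than the FAS that heads the table, without notice. SVR12 is expected to be near 100%, so one failure carries much of the information. If that failure were the lone genotype 4 subject, leaving it out could decide which side of -10% the bound falls. The study is also open label, so a handling rule chosen late might be chosen with results in view.

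**Working it through.** **The plan's own power figure.** Inputs from Section 1.3: 90 per group at 98%, 125 per group at 95%, margin 10%, one-sided 0.025. Power is about Φ(0.10/SE − 1.96), with SE = √(2p(1−p)/n).
- Cohort 1: SE = √(2×0.98×0.02/90) = 0.0209; 0.10/0.0209 − 1.96 = 2.83; power 99.8%.
- Cohort 2: SE = √(2×0.95×0.05/125) = 0.0276; 0.10/0.0276 − 1.96 = 1.67; power 95.2%.

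Exact enumeration gives 98.8% and 94.4%, so the claim of at least 90% holds for the planned sizes.

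**Weight of a one-armed stratum.** The MH weight is w = n₁n₂/(n₁+n₂). One subject against none gives 1×0/1 = 0. The estimate Σw·d/Σw stays defined, because the other strata carry the comparison.

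**How often it would happen.** Assumptions: 5% genotype 4 and 50% prior SMV, so each genotype 4 stratum has probability 0.025. The block size is not stated.
- Expected genotype 4 subjects among those dosed: 0.05×32 = 1.6 and 0.05×50 = 2.5.
- Chance of none at all: 0.95³² = 19% and 0.95⁵⁰ = 8%.
- Hand check with blocks of 2, where a genotype 4 stratum is one-armed only if it holds exactly one subject. Cohort 1 (34 randomized): P(exactly one) = 34×0.025×0.975³³ = 0.369; for either stratum, 1 − (1−0.369)² = 60%. Cohort 2 (53 randomized): 53×0.025×0.975⁵² = 0.355; 1 − (1−0.355)² = 58%.

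Simulation, with two undosed subjects removed at random from Group 1 and three from Group 4, gives the chance of at least one zero-weight subject:

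| Allocation | Cohort 1 | Cohort 2 |
|---|---|---|
| Blocks of 2 | 60% | 60% |
| Blocks of 4 | 66% | 68% |
| Blocks of 6 | 67% | 71% |
| Independent of stratum | 69% | 75% |

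The last row ignores the stratified schedule in Section 3.3 and is an upper reference only. When it happens, 1.2 to 1.8 subjects are lost on average. Over all the settings tried (prior SMV 30% or 50%, blocked or independent), the chance is 31-44% and 45-57% at 2% genotype 4, and 18-27% and 30-37% at 1%. It is essentially nil if no genotype 4 subject was enrolled.

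**What it changes.** The four-stratum interval was compared with one stratified by prior SMV only whenever a stratum lacked an arm. Outcomes were drawn at the SAP's 98% and 95%, with 5% genotype 4.
- The reading against -10% changes in 0.4-0.9% of Cohort 1 trials and 0.9-4.3% of Cohort 2 trials, in no consistent direction.
- The lower bound moves by more than 5 points in at most 2.1% of trials.
- A non-responder gets zero weight in 1.3-2.1% and 3.3-6.5% of trials.
- The mean half-width changes by 0.1 point or less with the plug-in or Sato variance, and falls by 0.3-0.7 points with the variance based on (x+0.5)/(n+1).

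**A bad case.** Suppose the only Cohort 1 failure is a lone genotype 4 subject in Group 1. The four-stratum difference is 0 with plug-in interval (0, 0). Stratified by prior SMV alone, it is -6.3% with lower bound -17.8%. Unstratified, 14/15 vs 17/17 gives -1/15 = -6.7%, SE = √(0.933×0.067/15) = 6.4% and lower bound -19.3%. The reading reverses.

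**The case for a change.** The best argument for a rule is that it is cheap and blind to outcome. One sentence, triggered by stratum counts alone, would remove discretion in an open-label study, would cost essentially no precision and would do nothing if never triggered. The bad case shows that a small average effect does not exclude a large one in a particular data set.

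The facts stand: the four strata, the arm sizes and the silence on one-armed strata are as described. Section 6.4.1 could not be read for this review, but the contents list gives it to the FAS definition, so a pooling rule there is unlikely.

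The inference is weaker. An analyst who follows Section 6.1.2 has no choice to make about the weights, because the MH formula sets them. The bad case is rare. Its (0, 0) interval also comes largely from the plug-in variance collapsing when every remaining subject responds, which a collapsing rule does not cure. With 15/15 vs 17/17, the plug-in lower bound is 0, while the variance based on (x+0.5)/(n+1) gives -11.8% with no stratum dropped.

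The rule also has a price. At 5% genotype 4 it would apply in about half to three quarters of cohorts. The analysis would then no longer follow the randomization factors, and the two cohorts or the two FAS versions could be stratified differently.

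**Conclusion.** No change is needed. The silence on one-armed strata is a missing detail that the estimator itself resolves, and following the plan as written still gives a sound conclusion.

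- **Reach.** It is confined to two comparisons that the SAP calls exploratory and too small for the test. The SVR12 rates and Clopper-Pearson intervals by group include every subject.
- **Visibility.** Tables 15.8.1.2, 15.9.4.7 and 15.9.4.8 and Figure 15.9.7 show counts or rates by stratum, and Listing 16.2.2.3 shows IWRS discrepancies. A reader can see a thin stratum.
- **Size.** One or two subjects per cohort, and a changed reading in under 1% (Cohort 1) or about 1-4% (Cohort 2) of trials, with no consistent direction.

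These sizes assume 5% genotype 4, 50% prior SMV, the SAP's response rates and allocation blocked within stratum. The actual genotype 4 count and the block size are not given. Fewer genotype 4 subjects make the issue less likely. A footnote in the report giving the number of subjects with zero weight would be courteous, but nothing depends on it.
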